**ANCOVA model:**

$\Delta$  in response rate compared to placebo and corresponding 95% CI will be estimated with SAS® GLM procedure using LSMEANS statement (see SAS code in Appendix 18.5). The ANCOVA will include baseline, region as covariates and treatment group as an independent variable.

Validity of the model will be verified as follows:

- The homogeneity of variances between treatment groups will be checked using the Levene's test. A scatter plot of residuals versus fitted values will be also performed.

- In order to assess the independence of error terms, a residual lag plot will be performed, ie constructed by plotting residual (i) against residual (i-1).
- A scatter plot of the response variable against the covariates, using separate symbols for each treatment group will be performed to verify the presence of linear relationship between the covariates and the response variable, and that all treatment regression lines have the same slope.
- Homogeneity of regression slopes will be verified by first running the model with the interaction between the covariates and the treatment group. This assumption will be validated if this interaction is not significant. If this assumption is verified, then the interaction will be removed from the model.
- Normality of residuals will be checked by computing Skewness and Kurtosis, which should fall within the interval [-2;2]. Normal QQ-plot of residuals will be performed as well.

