## **8.5 Description of Statistical Analyses**

### **8.5.1 General Considerations**

A general description of the statistical methods to be used to analyze the efficacy and safety data is outlined below. Prior to locking of the database for the study, a detailed SAP will be finalized.

Any changes to the data analysis methods described in the protocol will require an amendment only if a principal feature of the protocol is affected. Any other changes to the planned data analysis that does not require a protocol amendment will be described in the SAP and the CTR. Additional exploratory analyses will be conducted as deemed appropriate.

A 2-sided  $\alpha$  level of 0.05 will be applied for tests of treatment effect within the study.

For the purpose of statistical analyses, baseline is defined as the last assessment prior to first dose.

In general, continuous variables will be summarized descriptively using the number of observations (N), mean, standard deviation (SD), median, first quartile (Q1), third quartile (Q3), minimum, and maximum. Categorical variables will be summarized using frequency counts and percentages.

Statistical analysis will be performed using the computer program package SAS® System for Windows (version 9.4 or higher; SAS Institute, Cary North Carolina, USA).

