**Supportive analysis no. 1: Stratified difference of response rates 95% CI**

In order to further characterize the dose-response, the proportion of ACR20 response at Week 12 will also be presented for each treatment group, along with the stratified difference in ACR20 response proportion between each evobrutinib dose and placebo, and the 2-sided 95% CI for the difference [Evobrutinib – Placebo].

The following will be presented: stratified Δ between response rates for pairwise comparisons versus placebo, the 2-sided 95% CI, and nominal p-value. As there are 3 regions (Western Europe, US, ROW), the number of strata is equal to K=3.

For each pairwise comparison, the difference of response rate will be computed using the formula no. (7), available in Lu 2008. By denoting A the 1st treatment group (evobrutinib 25 mg QD, evobrutinib 75 mg QD or evobrutinib 75 mg BID) and B the treatment group of comparison (placebo), the difference in response rate is the weighted average of differences within strata. It can be written as

$$\hat{\delta} = \frac{\sum_{j=1}^K W_j (r_{Aj} - r_{Bj})}{\sum_{j=1}^K W_j}$$

, where  $r_{Aj}$  represents the response rate of the treatment group A in the strata j, and  $W_j$  represent the CMH weight of the stratum j. This CMH weight must be calculated using the formula no. (9), available in Lu 2008, and then standardized to have a sum equal to 1:

$$W_j^{CMH} = \frac{\left[ \frac{1}{n_{Aj}} + \frac{1}{n_{Bj}} \right]^{-1}}{\sum_{j=1}^K \left[ \frac{1}{n_{Aj}} + \frac{1}{n_{Bj}} \right]^{-1}}$$

, where  $n_{Aj}$  represents the sample size of the strata j for the treatment group A ( $n_{Bj}$  for treatment B respectively).

Once  $\hat{\delta}$  is calculated, the chi-square statistic is given by the formula no. (1), available in Lu 2008. Consider the following hypotheses  $H(\delta): \pi_{Aj} - \pi_{Bj} = \delta$  for  $j = 1, \dots, K$ , we obtain

$$X^2(\delta) = \frac{[\sum_{j=1}^K W_j (r_{Aj} - r_{Bj} - \delta)]^2}{\sum_{j=1}^K W_j^2 \tilde{V}_{r_{Aj} - r_{Bj}}}$$

where

$$\tilde{V}_{r_{Aj} - r_{Bj}} = \left\{ \frac{\tilde{R}_{Aj}(1 - \tilde{R}_{Aj})}{n_{Aj}} + \frac{\tilde{R}_{Bj}(1 - \tilde{R}_{Bj})}{n_{Bj}} \right\} \frac{N_j}{(N_j - 1)}$$

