**Table 16 : Analysis of the Other Secondary Endpoints at Week 12**

Endpoints	Analysis Set	Analysis method	Description	Missing data handling

 
EULAR Boolean remission
 
CDAI <math>\leq 2.8</math>
 
SDAI <math>\leq 3.3</math>
 
	
 
mITT set
 
	Primary analysis: Stratified $\Delta$	
 
Presentation of response rate for each treatment group, <math>\Delta</math> in response rate compared to placebo, 2-sided stratified MN 95% CI of <math>\Delta</math>
 
Summary statistics over time
 
	LOCF-NR*

 
EULAR Responder Index
 
	
 
mITT set
 
	Primary analysis for binary data: Stratified for $\Delta$	
 
Presentation of response rate for each treatment group, <math>\Delta</math> in response rate compared to placebo, 2-sided stratified MN 95% CI of <math>\Delta</math>
 
Summary statistics over time
 
	LOCF-NR*

 
EULAR Responder Index
 
	
 
mITT set
 
	Primary analysis for all categories: descriptive statistics	Summary statistics over time	LOCF-NR*

 
ACR hybrid score
 
DAS28-hsCRP
 
CDAI
 
SDAI
 
	
 
mITT set
 
	Primary analysis: Analysis of Covariance (ANCOVA) model	Presentation of adjusted means, adjusted $\Delta$ of means, associated 2-sided 95% CI of $\Delta$ .	LOCF (components)
		Supportive analysis: Hodges-Lehmann (HL) estimator	Presentation of difference median estimate and 95% CI (Asymptotic and exact)	
		Summary statistics	Summary statistics over time	

 
ACR components
 
	
 
mITT set
 
	Summary statistics	Summary statistics over time	LOCF (components)

 
ESR
 
	
 
mITT set
 
	Summary statistics	Summary statistics over time	As observed

\* LOCF-NR: post-baseline last observation carried forward. Patients who discontinued from treatment are considered as non-responders.

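### The ANCOVA for four supportive continuous endpoints drops treatment-by-covariate interactions only if they test non-significant, so the reported model hangs on a pre-test with no stated level or failure rule

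*SAP*

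**What the plan says.** SAP Table 16 gives the main method for ACR hybrid, DAS28-hsCRP, CDAI and SDAI as "Primary analysis: Analysis of Covariance (ANCOVA) model", and lists adjusted means, adjusted differences and 95% intervals as output. A Hodges-Lehmann analysis supports it.

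The ANCOVA text in SAP 14.2.2 starts from an additive model: "The ANCOVA will include baseline, region as covariates and treatment group as an independent variable". Estimates come from SAS GLM with LSMEANS; the code is referred to Appendix 18.5, where it is not visible because of redaction.

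A list of validity checks follows. One of them begins by fitting a larger model: "Homogeneity of regression slopes will be verified by first running the model with the interaction between the covariates and the treatment group". The check counts as passed when that test fails to reach significance, and the SAP then gives the consequence of passing: "If this assumption is verified, then the interaction will be removed from the model".

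The section does not state:

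- the significance level of the interaction test;
- whether baseline and region are tested separately or jointly;
- which model or contrast is reported if the test is significant.

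The only general level is in Protocol 8.5.1, where a two-sided "level of 0.05 will be applied for tests of treatment effect within the study". That sentence does not cover tests of model assumptions.

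**The concern.** The interaction is in the model at the first fit, and the only written route out is a non-significant test of that same interaction. Read literally, the term list behind the reported estimate is chosen by the data. Two consequences could follow.

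- Four closely related endpoints could be reported from different models purely by chance.
- The nominal 95% intervals make no allowance for the selection step. If a region-by-treatment term is retained, the LSMEANS difference may also become a different quantity: an equally weighted average over regions in place of one that follows the enrolled mix.

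The rest of the plan does not work this way. The primary logistic model (SAP 14.1) and the imaging mixed model (SAP 14.2.3) have fixed terms. SAP 14.3, Table 20 fits the treatment-by-region interaction in a separate model and presents only its p-value.

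**Working it through.** The plan gives no figure for this step, so there is none to reproduce. The size of the effect has to be derived under stated assumptions.

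**Inputs from the documents**

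- Regions: "As there are 3 regions (Western Europe, US, ROW), the number of strata is equal to K=3" (SAP 14.1, supportive analysis no. 1).
- Four arms, 1:1:1:1, 80 evaluable per arm (Protocol 8.1 and 8.2).
- Covariates: baseline and region (SAP 14.2.2). ACR hybrid is built from percentage change since baseline (SAP Table 28), so it has no baseline value of its own and at most the region test applies to it.

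**Assumptions**

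- A 5% level for the interaction test.
- Separate tests for baseline and region.
- Retention after a significant test.
- Equal LSMEANS weights over regions.
- Region shares as shown below, the same in every arm.

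**Step 1: chance of a false flag, per endpoint**

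- Two independent tests: 1 − 0.95² = 0.0975, about 10%.
- One test only: 5%.
- In simulation with two tests and no true interaction, at least one was flagged in 8.6% to 9.8% of runs, depending on the region split.

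**Step 2: precision if region-by-treatment is retained**

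With n per arm and region shares s₁, s₂, s₃, the additive contrast has variance 2σ²/n. The equally weighted contrast has variance (2σ²/n) × (1/9) × Σ(1/sₖ). The ratio of standard errors is therefore √(Σ(1/sₖ)/9).

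| Assumed shares (%) | Σ(1/sₖ) | SE ratio |
|---|---|---|
| 33/33/33 | 9.00 | 1.00 |
| 20/20/60 | 11.67 | 1.14 |
| 10/20/70 | 16.43 | 1.35 |
| 10/10/80 | 21.25 | 1.54 |
| 8/12/80 | 22.08 | 1.57 |
| 5/10/85 | 31.18 | 1.86 |

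**Step 3: simulation**

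The simulation used 80 per arm, baseline correlation 0.5, a true effect of −0.5 SD, no true interaction and 5,000 runs per split. As a check, the additive standard error should be √(2 × 0.75/80) = 0.137 SD, and the simulation gave 0.137.

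- 10/10/80, region interaction retained: the standard error rises from 0.137 to 0.207 SD and the estimate moves by 0.22 SD on average. Coverage is 85.8% in those runs, and 94.4% over all runs under the rule.
- Only baseline-by-treatment retained: standard error 0.136 against 0.137 SD, and the estimate moves by about 0.015 SD.
- Additive model fixed in advance: coverage 94.8% to 95.8% across the splits.

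**Step 4: if an interaction is real**

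Take an assumed 0.8 SD loss of effect in one region holding 10% of subjects, in one dose arm (10/10/80 split, 3,000 runs). The region test is significant in only 30% of runs. The enrolled-mix effect is −0.5 + 0.1 × 0.8 = −0.42, and the equally weighted effect is −0.5 + 0.8/3 = −0.23. The additive model averages −0.42. The rule averages −0.34, which is neither quantity.

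**The case against.** The strongest reply is that this is a model check and not a selection rule. The sentence sits in a list with Levene's test, residual plots and skewness and kurtosis, none of which has a stated consequence on failure. The additive model is named first. A reader might infer that the SAP orders a significant interaction to be kept. It does not say so, and that part of the reply stands. What remains is that removal is explicitly conditional on the test and the other branch is blank. Whichever way the sponsor meant it, the reported model is not fixed.

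Second, slopes belong naturally to a continuous covariate, and the accompanying scatter plot is there to check for parallel regression lines. The check may have been meant for baseline only. The text, however, says covariates in the plural and has just named region as one. Both readings are open. Under the baseline-only reading the numerical effect is negligible.

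Third, the inflation factors depend on equal region weights in LSMEANS. The GLM code is redacted, so a different weighting cannot be excluded. The region shares are not in the documents either, and with equal regions the ratio is 1.00.

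Fourth, a reader might multiply the risk over endpoints: seven tests would give 1 − 0.95⁷ = 30%. That is only an upper figure under independence. SDAI is CDAI plus hsCRP, and DAS28 shares the joint counts and patient global, so the true figure is lower. It also mixes in baseline tests, which hardly matter. The per-endpoint figure is the fair one.

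Fifth, the Hodges-Lehmann analysis of the same endpoints has no interaction step. That is some protection, but as described it adjusts for neither baseline nor region, so it does not replace a fixed ANCOVA.

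**Conclusion.** The point holds as a small specification defect. The ANCOVA for ACR hybrid, DAS28-hsCRP, CDAI and SDAI depends on an interaction pre-test with no stated level and no stated rule for a significant result.

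- **Frequency:** up to about 10% per endpoint by chance (5% where one covariate is tested), at an assumed 5% level with separate tests.
- **Consequence:** a standard error multiplied by 1.00 (equal regions), 1.35 (10/20/70) or 1.57 (8/12/80), but only if region is tested, the term is retained and LSMEANS weight regions equally. It is negligible if only baseline-by-treatment is retained.

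It would be tempting to conclude that the intervals for these endpoints are generally invalid. The figures do not support that: overall coverage under the rule was 94.4% in the 10/10/80 case, and the damage is confined to runs in which a region term is retained. Nor does the point reach the main conclusions. SAP 14.2 treats secondary analyses as supportive and nominal, Table 16 lists no p-value for these four endpoints, and neither the primary ACR20 model nor the key secondary analyses use this step. Confidence in the wording defect is high. Its practical size cannot be fixed without the region shares and the redacted code.

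**What to change.** Replace the conditional sentence in SAP 14.2.2 with a fixed rule. The reported model is always treatment + region + baseline, with the baseline term omitted for ACR hybrid, where no baseline value exists. Covariate-by-treatment interaction tests and slope plots are presented as diagnostics and do not change the reported model. If an interaction model is shown as a diagnostic, state how its LSMEANS weight the regions.

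The cost is a sentence or two of SAP wording before database lock. It needs no new data and does not affect the sample size or the primary analysis. An additive model reports an average effect over the enrolled mix and will not itself display a real interaction; the diagnostics serve that purpose. This matches how SAP 14.3 already handles treatment-by-region for the binary endpoints.

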#### **HL estimator:**

A sensitivity analysis will be performed using a non-parametric method. The Hodges-Lehmann difference median estimate and 2-sided 95% CI will be calculated with SAS® NPAR1WAY procedure using HL statement (see SAS code in Appendix 18.5). Asymptotic and exact CIs will be computed.

#### **Summary statistics:**

For each continuous endpoint, baseline value will be presented first. Then, for each time point, the following will be presented on subjects who have reached this time point: absolute value, CFB and percent CFB.

### **14.2.3 Imaging Endpoints at Week 4 and Week 12**

The following imaging endpoints will be presented on MRI and MRI PP analysis sets:

- CFB in OMERACT RAMRIS scores (designated hand, minimal assessed joints: wrist, MCP joints #1 to #5):
  - Synovitis score,
  - Bone marrow edema (osteitis) score,

CCI

OMERACT RAMRIS scores for synovitis, tenosynovitis, bone marrow edema (osteitis), and erosions (Ostergaard 2004, Ostergaard 2017) will be read centrally by 2 independent readers, who are blinded to treatment and dose assignment and to chronology of each time point. Discrepancies in RAMRIS scores between the 2 readers will be reviewed at a consensus adjudication session with both readers to reach a consensus score for the designated cases. At a minimum, the images with the top 10% discrepancies in scores between the 2 readers will be reviewed (refer to Imaging Guidelines for details of Adjudication and Selection of Cases for Adjudication). In case of further discrepancies after the adjudication process, the average between the results from the 2 readers will be considered for statistical analysis. In subject data listings, both results from the 2 readers will be presented as well as the average result.

In addition, the Total Damage Score and Total Inflammation Scores for both RAMRIS and RAMRIQ will be analyzed as well (Total Damage Score will not be computed for RAMRIQ). They are defined according to the following formulas (Peterfy 2016, Brett 2018):

CCI

**Table 17 : Analysis of Imaging Endpoints**

Endpoints	Analysis Set	Analysis method	Description	Missing data handling

 
RAMRIS scores
 
	
 
MRI Analysis set
 
MRI PP Analysis Set
 
	Primary analysis: MMRM	
 
Presentation of adjusted means, adjusted <math>\Delta</math> (Evobrutinib – Placebo) of means, associated 2-sided 95% CI of <math>\Delta</math>, nominal p-value.
 
Summary statistics over time
 
	All available data as observed (MAR)
		Supportive analysis #1: ANOVA model with repeated measures	
 
Presentation of adjusted means, adjusted <math>\Delta</math> (Evobrutinib – Placebo) of means, associated 2-sided 95% CI of <math>\Delta</math>, nominal p-value.
 
Summary statistics over time
 
	Missing data will be imputed using linear interpolation or linear extrapolation
		Supportive analysis #2: ANOVA model with repeated measures	
 
Presentation of adjusted means, adjusted <math>\Delta</math> (Evobrutinib – Placebo) of means, associated 2-sided 95% CI of <math>\Delta</math>, nominal p-value.
 
Summary statistics over time
 
	As observed
		
 
Lineplot
 
	
 
Lineplots will be presented for RAMRIS Synovitis and Osteitis only.
 
	As observed

**MMRM:**

The MAR are ignorable missingness. When missing data due to dropout are ignorable, the parameters of dropout and outcome processes are assumed to be distinct. Hence, likelihood-based methods can be used on the marginal distribution of the observed data for statistical inference. MMRM is a particular form of a mixed model analysis and is fitted within the ignorable likelihood paradigm.

The MRI endpoints (change from baseline) will be analyzed using the MMRM model, with treatment group, visit, and treatment by visit interaction as the main effects, baseline MRI assessment and region as covariates. The unstructured covariance matrix will be considered. Denominator degree of freedom will be computed using Kenward and Roger’s method (Kenward 1997).

The LSMEANS estimate of MRI mean change from baseline score, difference of the LS Mean from placebo, 2-sided 95% CI of the difference and nominal 2-sided p-value of the difference from the model contrast will be presented at each visit.

An example of SAS code is available in Appendix 18.5.

In addition, summary statistics of observed values, change and percent change from baseline will be presented at each visit for each treatment group.

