### 7.3.3 Prevention of Joint Structural Damage Progression

Joint structural damage will be assessed using MRI at Baseline and Weeks 4 and 12 in subjects participating in the MRI substudy.

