### **8.5.3.3 Imaging Data and Other Efficacy Endpoints**

Analysis of the change from Baseline scores of the MRI data will be performed on the appropriate analysis sets (MRI analysis set for the RAMRIS and CARLOS scores) using a Mixed Model for Repeated Measures, with treatment arm as factors, and randomization strata, and Baseline as

covariates. Missing data will be handled as MAR. Other imputation methods will be provided in the SAP as additional sensitivity analyses.

Analyses of all other efficacy endpoints will be exploratory in nature and details will be further provided in the SAP.

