**Table 18 : Analysis of HRQoL Endpoints at Week 12**

Endpoints	Analysis Set	Analysis method	Missing data handling

 
• HAQ-DI Total Score
 
	
 
• QoL set
 
	
 
• MMRM
 
	As observed

 
• SF-36 (Change in PCS, MCS scores, and their components)
 
• FACIT-Fatigue (Change in Total score over time)
 
 
CCI [Redacted]
	
 
• QoL set
 
	
 
• MMRM model
 
• Descriptive statistics
 
• Probability of achieving %CFB value or higher
 
• Logistic regression
 
	As observed

**MMRM model:** similar as in Section 14.2.3.

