**MMRM: PROC MIXED with SAS**

A mixed model can be performed with SAS using the following code below. This sample code assumes the treatment group is assigned in the following order:

- 1 = Placebo
- 2 = Evobrutinib 25 mg QD
- 3 = Evobrutinib 75 mg QD

- 4 = Evobrutinib 50 mg BID

CCI

CCI

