**Table 47: Time Windows for ACR components**

Treatment groups	Period covered	Interval (days) [Date of assessment – Date of first dose + 1]	Analysis Visit

 
• Placebo
 
• Evobrutinib 25 mg QD
 
• Evobrutinib 75 mg QD
 
• Evobrutinib 50 mg BID
 
	12-week treatment period	1	Day 1
		[ 2 ; 21 )	Week 2 – Day 14
		[ 21 ; 42 )	Week 4 – Day 28
		[ 42 ; 70 )	Week 8 – Day 56
		[ 70 ; 98 ]	Week 12 – Day 84

 
• Placebo/Evobrutinib 50 mg BID
 
• Evobrutinib 25 mg QD/Evobrutinib 50 mg BID
 
• Evobrutinib 75 mg QD/Evobrutinib 50 mg BID
 
• Evobrutinib 50 mg BID/Evobrutinib 50 mg BID
 
	OLE period	1	Day 1 – OLE
		[2 ; 270 )	Month 6 – OLE
		[ 270 ; 367 )	Month 12 – OLE

Table 48: Time Windows for SF-36, FACIT-Fatigue and CCI

Treatment groups	Period covered	Interval (days) [Date of assessment – Date of first dose + 1]	Analysis Visit

 
• Placebo
 
• Evobrutinib 25 mg QD
 
• Evobrutinib 75 mg QD
 
• Evobrutinib 50 mg BID
 
	12-week treatment period	1	Day 1
		[ 2 ; 42 )	Week 4 – Day 28
		[ 42 ; 70 )	Week 8 – Day 56
		[ 70 ; 98 ]	Week 12 – Day 84

 
• Placebo/Evobrutinib 50 mg BID
 
• Evobrutinib 25 mg QD/Evobrutinib 50 mg BID
 
• Evobrutinib 75 mg QD/Evobrutinib 50 mg BID
 
• Evobrutinib 50 mg BID/Evobrutinib 50 mg BID
 
	OLE period	1	Day 1 – OLE
		[ 2 ; 270 )	Month 6 – OLE
		[ 270 ; 367 )	Month 12 – OLE

CCI

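### As written, the MMRM gives baseline one coefficient across visits; a baseline-by-visit term would be a cheap improvement for the Week 12 RAMRIS and patient-reported scores

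*SAP*

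**What the plan says.** The MMRM paragraph of SAP 14.2.3 analyses change from baseline in the MRI scores "with treatment group, visit, and treatment by visit interaction as the main effects, baseline MRI assessment and region as covariates". On the covariance it adds: "The unstructured covariance matrix will be considered". Degrees of freedom are Kenward-Roger. Protocol 8.5.3.3 describes the same analysis as "using a Mixed Model for Repeated Measures, with treatment arm as factors, and randomization strata, and Baseline as" covariates. Neither text lists a baseline-by-visit term.

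SAP Table 18 (Section 14.2.4) applies an MMRM to HAQ-DI, SF-36 and FACIT-Fatigue, described only as "similar as in Section 14.2.3".

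Appendix 18.5 introduces sample code with "A mixed model can be performed with SAS using the following code below", but that code is redacted in the public copy. The SAP text calls it an example.

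The MRI visits are fixed in Protocol 7.3.3: "Joint structural damage will be assessed using MRI at Baseline and Weeks 4 and 12 in subjects participating in the MRI substudy". RAMRIS therefore has two post-baseline visits. SF-36 and FACIT-Fatigue have three (Weeks 4, 8 and 12). HAQ-DI has four (Weeks 2, 4, 8 and 12).

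On inference, Protocol 8.5.1 says that a two-sided "level of 0.05 will be applied for tests of treatment effect within the study", and SAP 14.2 makes all secondary analyses supportive, with nominal p-values and intervals.

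**The concern.** The model is flexible by visit in two places (the treatment effect and the covariance) and rigid in a third (the baseline slope). Change scores need not depend on baseline equally at Week 4 and Week 12. With equal SDs, the slopes are equal only if baseline correlates equally with both visits, and the documents give no reason to assume that it does. If the slopes differ, the pooled slope is drawn towards the visit with the smaller residual variance. The Week 12 contrast is then adjusted with a slope that is not the Week 12 slope.

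Week 12 is the visit of interest, the MMRM is the primary RAMRIS analysis, and it is the only method in Table 18 for the HAQ-DI total score. The two supportive RAMRIS ANOVAs list treatment and region without baseline, so they do not recover the precision. For DAS28, CDAI and SDAI, by contrast, SAP 14.2.2 uses a Week 12 ANCOVA with baseline, whose slope belongs to that visit. What is at stake is a modest, avoidable loss of precision.

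**Working it through.** **Inputs from the documents.** Two post-baseline MRI visits; 40 evaluable subjects per group and 11% dropout (Protocol 8.1); effect size 0.7, or 0.6 as the second case (Protocol 8.1); two-sided alpha 0.05. SDs and baseline-to-visit correlations are not given. Protocol 8.1 says that no high-quality RAMRIS data from a similar population were available. They are assumed below.

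**Step 1: the plan's own figure.** Protocol 8.1 states about 80% power at 0.7 and about 70% at 0.6 for a rank-sum test. Noncentral-t power with n multiplied by the lower-bound efficiency of 0.864 gives 81.8% and 69.1%, so the figures reproduce. Rank-sum tests simulated on normal data give 85.3% and 73.5%. These figures do not use the MMRM.

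**Step 2: formula.** With treatment-by-visit in the model and complete data, the Week 12 contrast is the difference in mean change minus slope times the difference in mean baseline. Hence

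SE ratio (common slope / visit slopes) = sqrt[1 + (b12 − b_common)² × var(baseline) / residual variance at Week 12].

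Under an unstructured covariance with residual SDs s4 and s12 and correlation r, the common slope gives Week 4 the weight

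w4 = (s12² − r·s4·s12) / (s4² + s12² − 2r·s4·s12),

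so b12 − b_common = w4 × (b12 − b4).

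**Step 3: assumed slopes.** Take baseline SD 4 and r = 0.6. With residual SDs 2.2 and 3.0, r·s4·s12 = 3.96 and w4 = (9 − 3.96)/(4.84 + 9 − 7.92) = 5.04/5.92 = 0.851. With both SDs 3.0, w4 = 0.5. For slopes −0.10 and −0.30 in the first case, the gap is 0.851 × 0.20 = 0.170 in size, and sqrt(1 + 0.170² × 16/9) = 1.025.

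| Slopes, Week 4 and Week 12 | SE increase, SDs 2.2 and 3.0 | SE increase, both SDs 3.0 |
|---|---|---|
| −0.10, −0.10 | 0% | 0% |
| −0.10, −0.20 | 0.6% | 0.2% |
| −0.10, −0.30 | 2.5% | 0.9% |
| −0.15, −0.40 | 4.0% | 1.4% |

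**Step 4: assumed correlations.** Take equal SDs at all visits. The slope of change on baseline is the correlation minus 1, and the Week 12 residual variance is 1 minus the squared baseline–Week 12 correlation. For the last row, w4 = 0.48/0.51 = 0.941, the gap is 0.941 × 0.30 = 0.282, and sqrt(1 + 0.282²/0.64) = 1.060. Power is by normal approximation at effect size 0.7 with 40 per group; the unadjusted comparison has 87.9%.

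| Correlations: baseline–W4, baseline–W12, W4–W12 | SE ratio | Power, visit slopes | Power, common slope |
|---|---|---|---|
| 0.8, 0.8, 0.8 | 1.000 | 91.0% | 91.0% |
| 0.8, 0.7, 0.8 | 1.005 | 92.4% | 92.2% |
| 0.7, 0.5, 0.7 | 1.014 | 95.1% | 94.6% |
| 0.8, 0.5, 0.7 | 1.046 | 95.1% | 93.3% |
| 0.9, 0.6, 0.7 | 1.060 | 93.8% | 91.0% |

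The most extreme case tried (0.9, 0.5, 0.6, with the SD shrinking to 0.8 of baseline by Week 12) gives 1.13. For SF-36 and FACIT-Fatigue with three visits, the ratio runs from 1.002 under mild decay of the correlation to 1.035 under AR(1) decay.

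**Step 5: simulation.** MMRM fits with four arms of 40 and 1,500 runs per scenario gave empirical SE ratios of 0.998, 1.005, 1.015, 1.047 and 1.062 for the five rows of Step 4, and 1.018 for the third row with 11% Week 12 dropout. Bias was 0.007 or less in absolute value under either model. Scores were normal and region was ignored.

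**The case against.** The strongest reply is that the public text cannot show what will be run. The MMRM code exists, the SAP's modification history says that it was corrected in version 2.0, and it may already contain the term. Redacted content is not missing from the plan, so a reader who infers that the analysis forces a common slope goes further than the documents allow. This stands as a limit on wording. It does not dispose of the point: the code is called an example, so the prose is the specification, and the prose lists one baseline term. For the patient-reported scores the link is looser still, since the model is only said to be similar.

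The second reply is that the loss is conditional. No passage shows that slopes differ between visits, and with equal slopes the cost is nil. The size also moves with the assumed SDs: in Step 3, equalising the residual SDs cuts 4.0% to 1.4%. This stands, and is why only a range can be given.

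Third, a common slope is a conventional and valid choice for a randomised comparison, and the endpoints are supportive. For SF-36 and FACIT-Fatigue, Protocol 8.5.3.4 plans only descriptive summaries. This also stands, and it keeps the point at the level of a cheap improvement.

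**Conclusion.** The point holds as a minor matter of efficiency and specification. As written, the MMRM has one baseline coefficient beside visit-specific treatment effects and an unstructured covariance. The Week 12 standard error is unaffected if the slopes are equal, about 0.2% to 1.5% larger under moderate slope differences and about 2.5% to 6% larger under strong ones. In the five scenarios of Step 4 that is 0 to about 3 points of power at effect size 0.7, and the common-slope model (91.0% to 94.6%) stays above both the unadjusted comparison and the planned 80%. All of this rests on assumed SDs and correlations.

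Three stronger readings are tempting and not supported:

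- A reader might turn the loss into a share of the sample by squaring the two largest ratios in Step 3 (1.025² = 1.05 and 1.040² = 1.08, so 5% to 8% more variance). That uses only the steepest slopes and ignores the rows at or near zero.
- A reader might infer that the common slope distorts the handling of missing visits. This is possible in principle, but no material bias appeared, including in the one scenario with dropout.
- A reader might infer that the MRI substudy is underpowered as a result. The stated power rests on an unadjusted rank-sum test and is untouched.

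**What to change.** In SAP 14.2.3, list the fixed effects as treatment, visit, treatment-by-visit, baseline, baseline-by-visit and region. State the same for the HAQ-DI, SF-36 and FACIT-Fatigue models in 14.2.4, in place of the loose cross-reference. Align the Appendix 18.5 code. If the code already contains the term, only the prose needs correcting. Make the change before database lock.

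The cost is one degree of freedom per extra visit: one for RAMRIS, two for SF-36 and FACIT-Fatigue, and three for HAQ-DI if all four visits are fitted. With equal slopes the term gains nothing, and the simulated ratio of 0.998 in that case shows that carrying it costs next to nothing. Sample size, data collection and blinding are unaffected.
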